**XXII. Institutional Review Board (IRB) Approval**

Subject enrollment and study related procedures will NOT be initiated until written study approval has been obtained from the UCSF/SF VAMC IRB.

We do not anticipate adverse events to be device attributable with use of the Vielight Neuro device. The device predecessor is currently sold as a general wellness device worldwide with no major adverse events having been reported to date. It satisfies the criteria of an unregulated low risk device defined by the FDA policy, "General Wellness: Policy for Low Risk Devices." However, should any Adverse Events or Serious Adverse Events (SAEs) occur during the study, these will be reported to the UCSF IRB immediately, within 5 working days of the PI's awareness of the event using an iRIS Adverse Event Reporting Form.

All SAEs need to be followed until the event is resolved (with or without sequelae). The PI will decide if more follow up information is needed in case the event is not resolved at study completion.

**XXIII. Data Protection:**

Loss of privacy may occur if research data are viewed by individuals outside the research team. We will minimize the risk of loss of privacy by training all research staff to maintain data in a secure manner and not to discuss study participants outside the research team. Research data will be stored in locked file cabinets or on VA-approved devices (e.g., VA-encrypted laptops) or secure VA servers. Study forms will include unique ID numbers but not names or other identifying information whenever possible. No names or other information that could identify subjects will be used for research of the data. A key that links each subject to a code number will be maintained in a database that is password protected and inside a secure computer network. Only the PI and designated staff working on this project will have access to the key. Signed consent forms will be kept in a locked cabinet and electronic information will be password protected

Consent forms and HIPPA records may be shared with the UCSF IRB and VA regulatory agencies during regular audits. Information about a subject's MRI may be shared with his/her physician if MRI abnormalities found.

## **STATISTICAL ANALYSIS PLAN**

We will use a two-sample t-test on the baseline vs. week-12 differences in PP cognitive measures to examine between-group differences to test hypothesis 1: Primary participants (PP) randomized to in the Immediate PBM group will show improvements in cognitive function after 12 weeks of near-infrared PBM therapy with the Vielight Neuro device compared to PP randomized to the Delayed PBM group.

We will also use a repeated-measures analysis of variance (ANOVA) to analyze the between-group differences in the ADAS-cog and NPI, with time (baseline, 6-, and 12-weeks) as the within-subject factor.

A functional connectivity analysis produced coefficients from a priori defined seed-voxel correlation with Pearson correlation analysis will be used. Fisher's r-to-z transformation will be used to convert correlation maps into z maps. Random effect models will be applied for second level analysis. A two-sample t-test on the baseline vs. week-12 differences between the Immediate PBM and Delayed PBM groups (Immediate [baseline-week 12] vs. Delayed [baseline-week 12]) will be used to examine the difference between the two groups for hypothesis 2: PP randomized to the Immediate PBM group will show increased functional connectivity within nodes of the DMN after 12 weeks of near-infrared PBM therapy with the Vielight Neuro device compared to PP randomized to the Delayed PBM group.

We will also use the CONN-fMRI Functional Connectivity toolbox version 17 to analyze the functional connectivity data. Default pre-processing parameters will be used to address the possible confounding effect of head motion artifacts and white matter (WM) and cerebral spinal fluid (CSF) blood oxygen level dependent (BOLD) signal. Blood oxygen level dependent (BOLD) signal noise from the WM and CSF will be characterized with the principal component-based noise-correctio 'CompCor' method utilized in the CONN toolbox. Band-pass filtering will be performed with a frequency window of 0.008 to 0.09 Hz. Region of interest (ROI) to ROI functional connectivity maps will be created for each participant. The mean BOLD time series will be computed across all voxels within each ROI. Bivariate-regression analyses will be used to determine the linear association of the BOLD time series between each pair of sources. Each scan will be Hanning weighted. We will use a predefined spherical ROI (with a radius of 10mm) from the CONN-fMRI Functional Connectivity toolbox as the seed to create connectivity maps of the DMN in the posterior cingulate cortex/precuneus (PCC) region, MNI coordinates 1, -61, 38, based on prior studies. For ROI-to-ROI analyses, a peak voxel threshold of  $p \leq 0.001$  and a cluster extent threshold of  $p \leq 0.05$  will be set for bidirectional explorations of connectivity (i.e., positive and negative associations).

We will extract the average cerebral blood flow (CBF) values for each subject by averaging the CBF values within a priori ROIs. Next, we will use a two-sample t-test on the baseline vs. week-12 differences between the Immediate PBM and Delayed PBM groups (Immediate [baseline-week 12] vs. Delayed [baseline-week 12]) to examine between-group differences for hypothesis 3: PP randomized to

Immediate PBM will show increased cerebral perfusion after 12 weeks of near-infrared PBM therapy with the Vielight Neuro device compared PP randomized to the Delayed PBM group.

We will also use a repeated-measures multivariate analysis of variance (MANOVA) to analyze the between-group differences in arterial spin labeled (ASL) perfusion MRI perfusion data, with time and ROI (superior frontal, superior parietal, supramarginal) as the within-subject factors. The ROIs (superior frontal, superior parietal, supramarginal gyrus) correspond to the locations of the transcranial LED clusters of the Vielight Neuro PBM device.

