(Immediate [baseline-week 12] vs. Delayed [baseline-week 12]) to examine between-group differences for hypothesis 2. We will use Spearman's rank correlation analysis to examine the relationship between baseline-to-week 12 changes in DMN functional connectivity and CBF with baseline-to-week 12 changes in ADAS-cog, MOCA, and QOL-AD in the Immediate PBM group to test hypothesis 3. We will use a two sample t-test on the baseline vs. week-12 differences in CG measures (i.e., Caregiver Burden Inventory, Positive Aspects of Caregiving Scale, Geriatric Depression Scale) to examine between-group differences to test hypothesis 5. We will also evaluate the magnitude of treatment effects on the PP and CG psychometric measures using Cohen d effect sizes for the within-group difference in the Delayed PBM group (baseline-to-week 12 and week 12-to-week 24).

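### No between-arm analysis adjusts for the baseline value; with 5 per arm, a chance imbalance leaves (r − 1) times the baseline difference in the change-score estimate, in favour of the arm that started worse

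*Combined protocol and SAP*

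**What the plan says.** Four hypotheses are tested on change from baseline to week 12, with no covariate named:

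- Hypothesis 1, cognition (SAP): "two-sample t-test on the baseline vs. week-12 differences in PP cognitive measures".
- Hypothesis 2, DMN connectivity (SAP): "A two-sample t-test on the baseline vs. week-12 differences between the Immediate PBM and Delayed PBM groups".
- Hypothesis 3, CBF (SAP): "we will use a two-sample t-test on the baseline vs. week-12 differences between the Immediate PBM and Delayed PBM groups".
- Hypothesis 5, caregiver measures (Protocol Summary, Statistical Methodology; not repeated in the SAP): "two sample t-test on the baseline vs. week-12 differences in CG measures".

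The SAP adds two between-arm analyses that are not t-tests. The first reads "We will also use a repeated-measures analysis of variance (ANOVA) to analyze the between-group differences in the ADAS-cog and NPI". Its repeated factor is the visit, at three levels: baseline, week 6 and week 12. The second reads "We will also use a repeated-measures multivariate analysis of variance (MANOVA) to analyze the between-group differences in arterial spin labeled (ASL) perfusion MRI", with time and ROI as within-subject factors. In the ANOVA, baseline is one level of the outcome. In the MANOVA the levels of time are not listed, but imaging is done only at baseline and week 12, so baseline must be one of them.

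Protocol section X sets 10 dyads, 5 per arm, with the number fixed by funding and device cost. Section XV describes no stratification or balancing. Section XIII sets no severity range. Section XIV places the psychometric baseline before randomisation, and the baseline MRI precedes treatment.

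**The concern.** A change score fixes the slope on baseline at 1. When r is below 1 (equal SDs at both visits), that slope over-corrects. The arm that starts worse is then expected to improve more, or decline less, through regression to the mean alone. With two groups of 5, no balancing and no severity limits, a sizeable baseline gap is likely.

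An imbalanced trial could therefore show a spurious effect or hide a real one. That bears on the first objective in section VII (Study Overview), which is to establish that encouraging results from an earlier study of 5 patients were not a chance finding. The two repeated-measures analyses give no protection. With baseline as an outcome level, the group-by-time term is again a comparison of changes, and the group main effect contains the baseline difference itself.

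**Working it through.** **Inputs.** From the documents: 5 per arm (section X); change-score t-test with 8 error df; baseline recorded for each outcome (section XIV). Assumed, because the documents do not give them: r from 0.3 to 0.9, equal SDs at baseline and week 12, normal data, all 10 participants complete, two-sided 0.05. The plan has no power or precision figure to reproduce. Everything below is in baseline-SD units.

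**How large the imbalance is.** The difference D between the two baseline means has SD √(2/5) = 0.632. Then P(|D| > 0.5) = 2[1 − Φ(0.5/0.632)] = 43%, and P(|D| > 1) = 2[1 − Φ(1/0.632)] = 11%.

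**What the change score does with it.** Given D, the expected week-12 difference under no effect is rD. Subtracting D leaves (r − 1)D. This has the opposite sign to D, so it favours the arm that started worse on any scale. The standard error of the change-score difference is √[0.4 × 2(1 − r)]. At D = 1 the shift in standard errors is therefore (1 − r)/√[0.8(1 − r)] = √[(1 − r)/0.8]: 0.94 at r = 0.3, 0.79 at 0.5, 0.61 at 0.7, 0.50 at 0.8 and 0.35 at 0.9.

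**Error rates and precision.** These come from simulation of 200,000 trials per r, comparing the change-score t-test (8 df) with ANCOVA of week 12 on group plus baseline (7 df).

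| r | Shift per 1 SD of imbalance | Change-score null rejection, imbalance > 1 SD | ANCOVA, same trials | Mean CI width ANCOVA/change, all trials | Same, imbalance > 1 SD |
|---|---|---|---|---|---|
| 0.3 | −0.7 | 15% | about 5% | 0.88 | 1.06 |
| 0.5 | −0.5 | 12% | about 5% | 0.95 | 1.14 |
| 0.7 | −0.3 | 9% | about 5% | 1.01 | 1.21 |
| 0.8 | −0.2 | 8% | about 5% | 1.04 | 1.25 |
| 0.9 | −0.1 | 6.5% | about 5% | 1.07 | 1.28 |

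Over all randomisations both tests reject at about 5% at every r. Of the change-score false positives in imbalanced trials, about 95% or more favour the arm that started worse for r up to 0.8, and about 86% at r = 0.9.

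**Break-even.** The expected variance ratio, ANCOVA to change score, is [(1 + r)/2] × 7/6, which equals 1 at r = 12/7 − 1 = 0.71. ANCOVA also pays for a larger critical value (2.365 on 7 df against 2.306 on 8 df), so average CI width breaks even lower, near r = 0.66 in simulation.

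**Power.** For a true effect of 1 baseline SD, change score to ANCOVA: 22% to 27% (r = 0.3), 29% to 32% (0.5), 44% to 44% (0.7), 59% to 57% (0.8), 87% to 82% (0.9). The t-test with 5 per arm reaches 80% power only for about 2.0 SDs of the change score.

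**The case against.** The strongest reply is that the planned test is valid. Randomisation makes it unbiased with 5% error, and the inflated rates apply only to the 11% of randomisations with more than 1 SD of imbalance. At r = 0.3 the other 89% reject at 3.7%, and 0.114 × 14.8% + 0.886 × 3.7% = 5.0%. This stands. The case for adjusting concerns the trial as it turns out, not the long-run error rate.

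The second reply is cost. ANCOVA estimates a slope from 10 people. In trials with imbalance above 1 SD its interval is 6–28% wider. At high r its root mean squared error there is also larger: about 0.50 against 0.46 at r = 0.8, and 0.36 against 0.30 at r = 0.9. Power for a 1-SD effect in those trials falls from 59% to 44% and from 86% to 69% respectively. At r of 0.3–0.5 ANCOVA has the smaller error. This stands too: at high r the choice is a trade-off. The documents do not settle r. Open severity criteria could raise it for cognition, and the one test-retest figure given (NPI, 0.79–0.86, section XIV) lies above break-even, though it is not stated to be a 12-week correlation. Nothing shows that r is high for every outcome.

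A reader might infer two stronger claims that the documents do not support. One is that every between-arm test is a t-test on change. The SAP also plans the ANOVA and MANOVA, which share the gap. The other is that baseline imbalance passes unreduced into the treatment estimate. A change score subtracts the imbalance and leaves only the (r − 1) part, with reversed sign.

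**Conclusion.** The point holds as a recommended improvement, not as an invalid analysis. No planned between-arm analysis uses the baseline value as a covariate. In the roughly one randomisation in nine with more than 1 SD of imbalance, the change-score test rejects a true null 6.5–15% of the time over r = 0.9 to 0.3, mostly in favour of the arm that started worse. ANCOVA holds about 5% there. It gains average precision below r of about 0.66 and loses a little above it. The sizes rest on the assumed r, equal SDs, normality, complete data and two-sided 0.05. Neither analysis makes 10 participants enough to detect a moderate effect.

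**What to change.** 1. In the SAP and the Protocol Summary, for each outcome with a stated between-arm t-test (ADAS-cog, MOCA, ROI CBF, CBI, Positive Aspects of Caregiving, GDS, and a summary DMN ROI connectivity value), pre-specify a model of the week-12 value on group plus that outcome's baseline. Report the adjusted difference with its 95% CI. Carry the hypothesis 5 analysis into the SAP.
2. In the ADAS-cog and NPI repeated-measures analysis, use weeks 6 and 12 as the outcome levels and baseline as a covariate.
3. In the ASL analysis, use week-12 CBF with ROI as the within-subject factor and baseline CBF as a covariate. Time then drops out, because only one follow-up scan remains. State whether the covariate is each ROI's own baseline or one average per participant, since several covariates cost more degrees of freedom.
4. Keep the change-score results as a sensitivity analysis.

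Two limits. QOL-AD has no stated between-arm t-test, so it is not on the list; adding it would be a new analysis. For voxel-level connectivity maps the baseline differs at every voxel, so the change is confined to summary ROI values.

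Cost: text changes and no new data; one error df (7 instead of 8). The average CI is about 12% narrower at r = 0.3, 5% narrower at r = 0.5 and 4–7% wider at r = 0.8–0.9, with the larger penalty in badly imbalanced trials given above.
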